5.8 Sample size calculation

The MCID for the KOOS at 2 years is 10 points(20, 21) and the standard deviation (SD) is approximately 18 in the population of interest.(20, 21) A total sample size of 176 participants (88 per group) will provide 90% power to detect an effect size of 10/18 (=0.56) SD with 5% statistical significance (two-tailed), allowing for up to 20% loss to follow-up.

The sample size calculation has not accounted for the repeated administrations of the KOOS after surgery. Assuming that each participant completes at least two questionnaires over the two years of follow-up (and at baseline) and that there is a moderate correlation of 0.7 between the repeated scores, the study will have 90% power to detect a difference of 0.25 SD in a longitudinal analysis.

6. Trial methods

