6.1 Description of randomisation and code breaking

6.1.1 Randomisation

Randomisation will be carried out intraoperatively once debridement of the chondral / osteochondral lesion has been performed and the true size of the defect can be measured. Once the size of the lesion has been confirmed to be no more than 4cm^2 , and therefore eligible for inclusion (see Section 5.5), randomisation will be performed. Consent and baseline assessment will be completed prior to surgery. Randomisation will be performed by a member of the local team not involved in data collection or participant follow-up using a secure internet-based randomisation system ensuring allocation concealment. The randomisation system will be available as part of the bespoke study database. Randomisation will be carried out by a member of the research team using their personal login details. Participants will be allocated in a 1:1 ratio to either microfracture plus microstructural scaffold (AMIC) or microfracture alone. The randomisation scheme will take into account important prognostic factors.

Any barriers to successfully randomising once debridement of the chondral/osteochondral lesion has been performed will be explored in phase 1 (internal pilot) of the RCT. Prospective surgeons have confirmed that there are not any foreseen issues around availability of instruments or materials with the above strategy.

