6.12 Likely rate of loss to follow-up

Until discharge from hospital, the only losses to follow-up will be due to death, a participant withdrawing or ceasing to engage in follow-up; these losses are expected to be very few. In estimating the target sample size for the study, a loss to follow-up of 20% has been allowed for.

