7.1 Plan of analysis – primary and secondary outcomes

Primary analyses will be by intention-to-treat (ITT) and will be directed by a pre-specified statistical analysis plan. Analyses will use data from all patients randomised. Primary and secondary outcomes will be compared using mixed model (continuous variables measured at multiple time points) regression, or logistic regression (binary variables). Mixed models allow all patients with data to be included in the analysis, i.e. partial missing data (assumed missing at random) is permitted. Interactions between treatment and time will be examined and if significant at the 10% level, results will be reported separately for each postoperative time point; otherwise overall treatment effects will be reported. Model validity will be checked using standard methods; if a model is a poor fit, alternative models or transformations will be explored. Outcomes analysed on a logarithmic scale will be transformed back to the original scale after analysis and results presented as geometric mean ratios. Analyses will be adjusted for baseline values and centre and surgeon will be fitted as a random effect. Findings will be reported as effect sizes with 95% confidence intervals, and in accordance with the CONSORT reporting quidelines.

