7.5 Health Economics

A prospective within-trial economic evaluation will be conducted from an NHS and personal social services perspective (PSS) at 2 years, following NICE guidelines.(22) Given the important economic consequences to society of delivering treatments to this younger patient group, we will also report productivity losses of absenteeism and presenteeism captured within the WPAI, and privately incurred costs separately. The economic evaluation will estimate the differences in the costs and health benefits between the two groups within a cost-consequences framework. Consequences of interest are quality adjusted life years (QALYs) and the primary and secondary outcomes.

The cost-effectiveness analyses will be by ITT and follow closely the statistical analysis in terms of methods to adjust for stratification and baseline variables. Costs and QALYs in the second year of treatment will be discounted using the discount rates advised in NICE guidelines (currently 3.5%).(22) It is likely that there will be a relationship between costs and outcomes and data are not missing completely at random but can be predicted by known confounders. Missing cost and QALY data will be jointly imputed using multiple imputation methods with chained equations assuming data and the primary economic analyses will use complete datasets with imputed data.

We will also report all available cost and outcomes, including QALY data, in a cost-consequences table for transparent decision-making, with costs aggregated by secondary care and community based NHS resources, PSS, productivity losses, and private expenses, and further aggregate the NHS plus PSS for the main analysis. The primary economic result will be the incremental net monetary benefit statistic, which represents the monetary value of an

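### The adjustment terms in section 7.1 omit the randomisation factors that 6.1.1 uses and that 7.5 implies the statistical analysis adjusts for

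*Protocol*

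**What the plan says.** Three places in the protocol bear on this.

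- Section 6.1.1 describes 1:1 allocation and adds: "The randomisation scheme will take into account important prognostic factors". The factors are neither named nor counted, and the section does not say whether they act through stratification or minimisation.
- Section 7.1 gives mixed models for continuous outcomes measured repeatedly and logistic regression for binary ones, and states the adjustment: "Analyses will be adjusted for baseline values and centre and surgeon will be fitted as a random effect". It also says that a pre-specified SAP will direct the analyses.
- Section 7.5 says the cost-effectiveness analyses will "follow closely the statistical analysis in terms of methods to adjust for stratification and baseline variables". Further on, it again has the differences in costs, QALYs and net benefit adjusted for both kinds of variable, in line with the statistical analysis.

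**The concern.** Section 7.5 attributes to the statistical analysis an adjustment that section 7.1 does not list. An SAP author working from 7.1 would leave the randomisation factors out; one working from 7.5 would put them in. Section 5.4(e) relies on exactly these two sections as the pre-specified plan that guards against reporting bias, so they should describe the same covariate set.

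The statistical reason for settling it is standard. Balancing the arms on a prognostic factor reduces the true sampling variance of the treatment difference. A linear model that omits the factor leaves its variance in the residual, so the reported standard error does not reflect the gain: the interval is too wide and the test rejects less often than its nominal level.

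**Working it through.** **1. The plan's own figure.** Inputs from section 5.8: "The MCID for the KOOS at 2 years is 10 points"; "the standard deviation (SD) is approximately 18 in the population of interest"; 90% power; "5% statistical significance (two-tailed), allowing for up to 20% loss to follow-up". Section 6.12 confirms the 20%.

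- Normal approximation: n = 2 × (1.960 + 1.282)² × 18² / 10² = 68.1, so 69 per group. 69 / 0.8 = 86.25, so 87 per group and 174 in total.
- Exact two-sample t: power is 0.8997 at 69 per group and 0.904 at 70, so 70 are needed. 70 / 0.8 = 87.5, so 88 per group and 176 in total.

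The stated 176 reproduces. It uses no covariate adjustment, so nothing below changes it.

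**2. Formulas.** Let R² be the share of outcome variance that the randomisation factors explain beyond the terms already in the model. The protocol gives no value, so a range is assumed, including zero. Take 70 analysed per group, a residual SD of 18 without the factors, and arms well balanced on them.

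- Reported SE without the factors: s = 18 × √(2/70) = 3.04 points.
- True SE: s × √(1 − R²). Ratio of reported to true: 1/√(1 − R²).
- Actual two-sided type I error without the factors: 2 × [1 − Φ(1.96/√(1 − R²))].
- Power at 10 points without the factors: 1 − Φ[(1.96 s − 10)/(s√(1 − R²))].
- Power at 10 points with the factors: Φ[10/(s√(1 − R²)) − 1.96].

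**3. Results.** The 95% CI half-width without the factors is 1.96 × 3.04 = 5.96 points in every row.

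| Assumed extra R² | SE too large by | Type I error, factors omitted | Half-width, factors included | Power, omitted | Power, included |
|---|---|---|---|---|---|
| 0 | 0% | 5.0% | 5.96 | 90.8% | 90.8% |
| 2% | 1.0% | 4.8% | 5.90 | 91.0% | 91.3% |
| 5% | 2.6% | 4.4% | 5.81 | 91.3% | 92.1% |
| 10% | 5.4% | 3.9% | 5.66 | 91.9% | 93.4% |
| 20% | 11.8% | 2.8% | 5.33 | 93.1% | 95.7% |

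**4. Simulation.** 140 analysed, four strata, permuted blocks of four, 6,000 runs, one continuous outcome with total SD 18. At R² = 10% the mean reported SE is 3.04 without the strata and 2.88 with them, against a true sampling SD of about 2.9. Type I error is 3.7% against 4.9%, and power at 10 points is 92.0% against 93.5%. At R² = 0 both analyses give a type I error of 4.9%. This agrees with the formulas.

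**The case against.** The case against is substantial, and most of it limits what can be claimed.

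- **A reader might infer that 7.1 excludes the factors.** It does not say so. The list is not declared closed, and the section defers to an SAP that is not among the documents. Section 7.5 suggests that adjustment for stratification variables is intended. For the same reason, one cannot conclude that the clinical and economic results will come from differently adjusted models.
- **A reader might infer that the standard errors are too large as a matter of fact.** The factors are unnamed. They may be centre itself, or be largely captured by surgeon or baseline score, and then nothing is lost. The size depends on an R² that the protocol does not give.
- **A reader might infer that planned power is lost.** It is not: power at 10 points exceeds 90% in every row, and the error is on the conservative side.
- **A reader might extend the argument to the binary outcomes.** It does not carry over. In a logistic model, omitting a prognostic covariate pulls the odds ratio towards 1, and adding one usually raises its standard error.

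A covariate list is also something a protocol may leave to its SAP. Had 7.1 been silent on covariates, there would be no point to make. But 7.1 states a set, and 7.5 describes the statistical analysis as adjusting for more. That mismatch stands.

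**Conclusion.** Sections 6.1.1, 7.1 and 7.5 are not aligned on whether the randomisation factors enter the models, and they should be. The consequence is conditional: it arises only if 7.1 is applied literally and the factors explain KOOS variance beyond baseline score, centre and surgeon. On the assumed range of extra R² from 0 to 20%, the standard error for a continuous outcome is then between 0 and 11.8% too large. The treatment estimate is unbiased, the false-positive risk is not raised, and neither the sample size of 176 nor the planned 90% power is called into question.

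The figures treat the 2-year KOOS as a single linear-model comparison with residual SD 18. Adjustment for baseline score would lower that SD and change the half-widths and power, but not the SE ratios, because R² is defined beyond the terms already fitted. This is a modest but free gain in precision and a consistency correction, not a defect in the validity of the primary analysis.

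**What to change.** Add one sentence to section 7.1: the models for KOOS and the other continuous outcomes also adjust, as fixed effects, for every factor used in the randomisation scheme that is not already in the model. If centre is one of those factors, it stays as the random effect and is not entered a second time. Word section 7.5 so that it refers to the same set.

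If the factors are unnamed to protect concealment, the protocol can refer to them generically and the SAP can name them. For the logistic models, limit the adjustment to what the event counts support, since complications may be too few to carry every factor.

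The cost is a sentence in 7.1 and a matching phrase in 7.5. The factors have to be known at randomisation, so no new data are needed, and the sample size does not change.

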7.2 Subgroup analyses

No subgroup analyses are planned

7.3 Frequency of analyses

The primary analysis will take place when follow-up is complete for all recruited patients, i.e. at 2 years. An analysis of outcomes at 1 year will also be conducted and reported. The value of including a closed formal interim analysis will be discussed with the DMSC. Safety data will be reported to the DMSC every 6 months, together with any additional analyses the committee request.

7.4 Criteria for the termination of the trial

There are two conditions that might lead the Trial Steering Committee (TSC) to recommend stopping the trial early:

- A) A failure to recruit sufficient patients or open sufficient sites to meet the target sample size within the proposed duration of the grant and refusal of the funder to extend the duration of recruitment.
- B) A failure to deliver the intervention as planned.

With respect to (A), we plan to recruit our target sample size of 176 participants over 24 months. After 8 months of active recruitment in the first 8 of our planned 16 study centres, opened in a staggered fashion, if our target recruitment rate is being met, we should have recruited 24 participants. Accepting recruitment typically starts slowly and increases over time as the trial gets established and that there is some variability from one month to the next (e.g. recruitment is typically lower over Christmas and in the summer holiday period than at other times of year) we will propose a recovery plan if:

- A) Between 18 and 24 patients have been recruited within 8 months and
- B) At least 5 sites have opened to recruitment

If these targets have not been met, i.e. fewer than 18 patients have been recruited or less than 5 sites have opened to recruitment, close down will be considered. Progression criteria are detailed in table 2.

The trial team will prepare a report for the TSC to consider and make a recommendation to the NIHR-HTA. With respect to (B), failure to deliver the intervention and rehabilitation as planned, we will monitor adherence to the protocol throughout the trial and will investigate all cases of nonadherence. We will prepare a report for the TSC to consider and we will propose halting the trial if the reasons for non-adherence cannot be addressed satisfactorily.

In addition to monitoring recruitment and adherence, the DMSC will monitor safety outcomes. The DMSC may recommend stopping the trial if the accrued data suggest that the trial is unsafe for one or both groups of participants.

Table 2 Progression criteria

	Red	Amber	Green
Trial recruitment	75%	75<100%	≥100%
Recruitment rate/ site/ month	0	0-1	≥1
Number of sites opened	<5	5<8	8
Total number of participants recruited	<18	18<24	24

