5.2 Trial design

Multicentre, parallel group, superiority randomised controlled trial (RCT) in which participants and clinical care teams (except for staff involved in the surgery) and members of the research team responsible for data collection will be blinded to allocation.

Phase 1 (internal pilot) will determine the feasibility to randomise once debridement of the chondral/osteochondral lesion has been performed. Progression to Phase 2 will depend on showing satisfactory recruitment in Phase 1. All participants from phase 1 to 2 will be followed up for 24 months. Progression will be contingent on meeting the criteria defined in section 7.4.

Further follow up may continue for up to 10 years subject to further funding.

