6.8 Planned recruitment rate

6.8.1 Phase 1

Phase 1 recruitment will take place in up to 8 sites for 8 months. There will be a review of the progression criteria at the end phase 1. See section 7.4.

6.8.2 Phase 2

If the progression criteria are met, recruitment into Phase 2 will continue in an additional approximately 8 sites (at least 16 sites total). All participants will be followed up for 24 months.

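### Protocol Table 2: the per-site recruitment-rate row does not fit the pilot target of 24 participants; green at 1 or more is set too high for any ordinary opening schedule, and red at 0 cannot flag a failing pilot

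*Protocol*

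**What the plan says.** Section 5.2 ties the move to Phase 2 to the pilot criteria: "Progression will be contingent on meeting the criteria defined in section 7.4". Section 7.4 gives the overall target, "we plan to recruit our target sample size of 176 participants over 24 months". It also sets the pilot target, judged at month 8 on half of the 16 centres, which are to be "opened in a staggered fashion, if our target recruitment rate is being met, we should have recruited 24 participants". Section 6.8.1 agrees on the size of the pilot: "Phase 1 recruitment will take place in up to 8 sites for 8 months". Section 6.8.2 adds about 8 sites in Phase 2, for a total of 16 or more.

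The text of section 7.4 then states a rule that uses only two quantities. A recovery plan is proposed with 18 to 24 participants and at least 5 open sites; closing down is considered with fewer than 18 participants or fewer than 5 sites.

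Table 2 has four rows: trial recruitment as a percentage, rate per site per month, sites opened, and participants recruited. In the order red, amber, green, the rate row reads "Recruitment rate/ site/ month 0 0-1 ≥1". The participant row is red below 18, amber from 18 to below 24, and green at 24. The sites row is red below 5, amber from 5 to below 8, and green at 8. No rule says how the four rows combine, and neither the per-site target rate nor the opening schedule is stated.

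**The concern.** The count, the number of sites and the per-site rate are not free of one another. Once the months that sites have been open are known, a participant count fixes the average rate. So the rate row has to agree with 24 participants at the green end and with 18 at the red end, and it appears to do neither. Green at 1 asks for more than the plan needs, and red at 0 is reached only if nobody at all is recruited.

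The Trial Steering Committee reviews recruitment formally at the end of Phase 1, on criteria that decide whether the trial continues. It could receive three green rows and one amber from a pilot that is exactly on plan, or a red count beside an amber rate, with nothing in the protocol to say which row prevails. The table also contains a criterion that the text rule does not mention, so table and text differ on what the criteria are.

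**Working it through.** **Inputs.** From section 7.4: 24 participants after 8 months in 8 staggered sites; 176 participants in 24 months; 16 planned sites. From Table 2: participant limits of 18 and 24; rate limits of 0 and 1. The opening schedule is not in the protocol and has to be assumed.

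**Formula.** Average rate = participants / open site-months.

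**Reproducing the plan's own figures.** Assume that one site opens at the start of each month until 16 are open.

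- Pilot site-months: 8 + 7 + ... + 1 = 36. Target rate: 24/36 = 0.667.
- Whole-trial site-months: 24 + 23 + ... + 9 = 264. Target rate: 176/264 = 0.667.
- Phase 2 alone: 264 - 36 = 228 site-months and 176 - 24 = 152 participants; 152/228 = 0.667.

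A single rate of two-thirds thus returns both stated totals exactly.

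**Range over opening schedules (pilot, 8 sites, 8 months).**

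| Opening schedule | Site-months | Rate for 24 | Rate for 18 | Participants at a rate of 1 |
|---|---|---|---|---|
| All 8 open from the first day | 64 | 0.375 | 0.281 | 64 |
| One per month, start of month | 36 | 0.667 | 0.500 | 36 |
| One per month, mid-month | 32 | 0.750 | 0.563 | 32 |
| One per month, end of month | 28 | 0.857 | 0.643 | 28 |

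The rate that delivers 24 is below 1 in every row.

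**When would green at 1 agree with 24 participants?** Only if 24 / site-months is at least 1, that is, with at most 24 site-months. Over 8 sites this is 24/8 = 3 of the 8 months each on average. If that rate of 1 then continued, the 8 pilot sites would supply 8 x 16 = 128 of the 152 participants still needed in the remaining 16 months. The 8 new sites would have to supply only 24, or 3 months each out of 16.

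**Size at the green end.** With one site opening per month, a rate of 1 gives 36 participants in the pilot instead of 24 and 264 in the trial instead of 176. In both cases this is 50% above the target.

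**Red end.** This needs no schedule. With 1 to 17 participants the rate is above 0, so the rate row is not red; the participant row is red. For illustration, on 36 site-months a rate of 0.25 gives 9 participants: amber on rate, red on count. On that schedule the participant limit of 18 corresponds to 18/36 = 0.50, not 0.

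**Bands.** As printed, a rate of 0 falls in both red and amber, and a rate of exactly 1 in both amber and green.

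**The case against.** Four points can be made for the plan.

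1. A reader might infer that Table 2 rates an on-target pilot amber as a whole, or lets a failing pilot escape red. The document does not support either reading. There is no combination rule, so an on-target pilot is amber on one row and green on three. A pilot below 18 participants is red on the count row and meets the condition in the text for considering close-down. This stands, and it limits the consequence.

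2. The text rule never uses the rate, and the outcome is a report to the steering committee and a recommendation to the funder, not an automatic stop. This also stands. It shows that the row is not needed, but not that it is right: section 5.2 makes progression depend on section 7.4, and section 7.4 refers to Table 2 for the criteria.

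3. The figure of 0.67 is an inference, because no schedule is given. That is correct, and it must be labelled so. The conclusion at the green end does not depend on 0.67 itself, since the rates tried run from 0.375 to 0.857. A schedule with 24 or fewer site-months would remove that conflict, so it cannot be said that green on all rows is impossible. The red end does not depend on the schedule.

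4. The row might mean the rate reached at the time of review, not the pilot average; section 7.4 expects recruitment to start slowly and rise. The protocol does not say so. If this is meant, it has to be defined. It would not repair the red limit.

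**Conclusion.** The rate row of Table 2 is inconsistent with the other rows and with the pilot target in section 7.4. At the green end, 1 per site per month compares with about 0.67 if one site opens per month. That schedule is an assumption, but it reproduces both 24 at month 8 and 176 at month 24; the other schedules tried give 0.375 to 0.857. All of these treat the rate as the average over open site-months. Green at 1 fits 24 participants only with at most 24 site-months. An on-target pilot would therefore normally be amber on this row alone.

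At the red end, the limit of 0 cannot identify any pilot with 1 to 17 participants, whatever the schedule. The participant row and the text rule still do, so a failing pilot would not go unnoticed. The defect is a wrongly set threshold in a stop/go table: limited in consequence, wrong as written, and easily corrected.

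**What to change.** Choose one of two changes.

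- **Delete the row.** Table 2 then rests on participants and sites, as the text of section 7.4 does; the percentage row restates the participant count against its target. This is the simpler choice.
- **Keep the row and define it.** State the rate as participants randomised per open site-month over Phase 1. Counting randomised participants matters because consent precedes surgery and eligibility is settled only in theatre. Set green at 24 divided by the site-months in the sponsor's planned opening schedule, red below 18 divided by the same number, and amber between, with bands that do not overlap. If one site opens per month the limits are 0.67 and 0.50.

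The limits 0.67 and 0.50 should not be written in without checking the schedule. With all 8 sites open from the start, 24 participants would be 0.375 and so red on such a row while green on the count row, which recreates the conflict.

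The cost is one table row in a protocol amendment, agreed with the Trial Steering Committee and the funder.
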